#### ***e. Blinding***

It is not feasible to blind staff or patients as to the procedure. Study data will be blinded for the purposes of analyses, assigned as group 1 or group2 rather than prone / not prone.

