## 6. **Study outcome measure**

### a. **Primary outcome measure**

Requirement for invasive mechanical ventilation or death by 28 days post enrolment

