### b. **Secondary outcome measure**

- Length of time tolerating prone positions measured in minutes from prone to request to return to supine position or emergency repositioning if required
- SpO2 : FiO2 ratio (as a surrogate marker of P/F ratio) measured before proning and 1 hours after proning or P/F ratio where arterial line available
- Number requiring increase in ventilatory assistance (CPAP+BIPAP+IMV etc)

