#### ***b. Analysis population***

Data will be analysed on an intention to treat basis with all data for patients who consented to be involved included in baseline data analysis. Outcome data will be analysed for all patients who were positioned in the prone position for any length of time. A further per protocol analysis will be carried out on all patients who tolerated at least 1 hour of the daytime proning time and at least 2 hours of the night time proning period in any 24 hour period. Patients who were rescue prone will be considered a protocol deviation and will be studied as a group. Definition of the two groups: The

patients who receive the prone positioning are classified as prone positioning group. The patients who receive HFNC alone are classified as HFNC group. Comparisons between the two groups: Quantitative continuous variables are given as either means ( $\pm$ SDs) or medians (with inter-quartile ranges) are compared using the unpaired Student's t test or the Mann-Whitney test. Qualitative or categorical variables are compared with the chi square test or the Fisher's exact test. ANOVA for paired tests to compare the same variables collected at different time points are used. The cumulative probability of remaining on spontaneous breathing are compared with the Kaplan-Meier estimate of survival and the log-rank test to compare the two groups. Univariate and multivariate analyses of risk factors for PP failure are performed with logistic regression. All analyses are in intention to treat, and the level of significance is set at 0.05.

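### Group 1 / group 2 labels do not mask an analyst who also holds the proning data; masking is achievable for the primary and ventilatory-assistance outcomes, but section 9e does not set it up and section 11b blocks it

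*Combined protocol and SAP*

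**What the plan says.** Section 9e accepts that staff and patients cannot be blinded, then states: "Study data will be blinded for the purposes of analyses, assigned as group 1 or group2 rather than prone / not prone". It names no holder of the code, no restricted dataset, no order of release and no point of unblinding.

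The primary outcome (6a) is "Requirement for invasive mechanical ventilation or death by 28 days post enrolment". Section 6b lists three secondary outcomes:

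- "Length of time tolerating prone positions measured in minutes from prone to request to return to supine position or emergency repositioning if required";
- the S/F ratio "measured before proning and 1 hours after proning or P/F ratio where arterial line available";
- the number of patients who need more ventilatory assistance.

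Section 9d allocates controls to high-flow nasal cannula without prone positioning.

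Section 11b declares intention to treat, at its start and again at its end. Between those statements it says: "Outcome data will be analysed for all patients who were positioned in the prone position for any length of time". It also defines a per-protocol set by hours proned (1 hour by day and 2 by night), treats rescue-proned patients as deviations to be studied as a group, and defines the two comparison groups by the treatment patients receive.

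**The concern.** Coded labels mask an analyst only if nothing else in the file tracks the arm. Here several required variables do, because routine proning occurs in one arm by design.

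Two things are at stake. First, masking at analysis is the only masking the plan offers. If it is not delivered, a report that the analysis was blinded would be wrong. Second, masking keeps the direction of the effect from the analyst until the primary result is fixed. Some decisions are still open when the data are opened: section 11b allows either the chi-square or Fisher's exact test for categorical variables, and it gives conflicting definitions of who is analysed. An analyst who knows the arms would make those decisions with the direction of effect in view.

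**Working it through.** **The plan's own figure.** The blinding statement carries no number. The illustration below takes its arm size from section 11a, so that figure was checked first. With 60% v 40%, two-sided alpha 0.05, 80% power, pooled variance under the null and no continuity correction:

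n = [1.960 × √(2 × 0.5 × 0.5) + 0.842 × √(0.6 × 0.4 + 0.4 × 0.6)]² / 0.2² = 96.9, rounded up to 97 per group.

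This matches the plan. Recruiting 196 gives 196 / 2 = 98 per arm.

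**Which analyses need a proning variable?**

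| Item | Section | Needs proning data? |
|---|---|---|
| Invasive ventilation or death by day 28 | 6a | No |
| Increase in ventilatory assistance | 6b | No |
| Minutes prone | 6b | Yes |
| S/F or P/F before and 1 hour after proning | 6b | Yes; no time zero is given for controls |
| Set proned for any length of time | 11b | Yes |
| Per-protocol set | 11b | Yes |
| Rescue-prone group | 11b | Yes |
| Groups by treatment received | 11b | Yes |
| Intention-to-treat set by allocation | 11b | No |

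Two of the three secondary outcomes, and every set or grouping in 11b other than intention to treat, depend on proning data.

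**Could rescue proning of controls hide the arm?** The documents give no rates, so these are assumptions. Let X be the number ever proned in the prone arm, Binomial(98, q), and Y the number in the control arm, Binomial(98, r). Expected counts are 98q and 98r. With q from 80% to 100% and r from 0% to 30%, they are 78.4 to 98 in one coded group and 0 to 29.4 in the other. Counting by code fails to identify the arm only if Y ≥ X:

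P(Y ≥ X) = Σₓ P(X = x) × P(Y ≥ x)

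| q | r | Expected counts | P(Y ≥ X) |
|---|---|---|---|
| 80% | 30% | 78.4 v 29.4 | 3.1 × 10⁻¹⁴ |
| 70% | 40% | 68.6 v 39.2 | 1.0 × 10⁻⁵ |

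Even heavy crossover leaves the arm identifiable from one tabulation.

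**Does this reach the primary analysis?** That depends on which sentence of 11b governs.

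- *Intention to treat by allocation.* The primary set needs only the coded arm, so a file without proning fields is enough.
- *The any-proning set.* Proning status is needed before the primary set can be formed, so the analyst or whoever builds the file must use it.
- *Groups by treatment received.* The group variable is then itself a proning flag. Taken together with the any-proning set, this leaves no patient treated with high-flow oxygen alone in the outcome data, and so no comparison to mask.

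The plan states all three.

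**The case against.** The strongest reply is that section 9e does not say the analyst receives the proning fields along with the primary data. It is silent on procedure and does not prescribe one that fails. The primary and ventilatory-assistance outcomes contain nothing that identifies the arm, and an intention-to-treat set can be built from coded allocation alone. This stands, and it limits the point: masking is possible for those two outcomes.

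Three stronger inferences are tempting, and the documents do not support them.

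- A reader might infer that no blinded analysis is possible. The two outcomes above show otherwise.
- A reader might infer that masking is lost for every patient as soon as the data are opened. That assumes a single file holding everything, which the plan neither states nor rules out.
- A reader might take the choice between chi-square and Fisher as the size of the harm. By exact enumeration at 98 per arm and 60% v 40%, power is 81.3% for the uncorrected chi-square and 77.2% for Fisher, and the two disagree about p<0.05 in 4.1% of trials. But both two-sided p-values are unchanged if the codes are swapped, so a fully masked analyst faces the same choice. The gap arises because no test is named, and withholding proning fields would not remove it.

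Other open choices add little. The t test or Mann-Whitney option concerns continuous variables, not the binary primary outcome. The plan does state how rescue-proned patients are classified. The risk-factor model for failure of proning concerns proned patients, where masking has no role.

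The objection does not answer the main point. Silence on access, release order and code-holding means that relabelling alone does not secure what 9e promises, and the conflict in 11b leaves open whether the primary set can be formed without proning data.

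**Conclusion.** The concern holds in a limited form. Group labels do not mask an analyst who also has proning data. For minutes prone, oxygenation around proning, and the any-proning, per-protocol and rescue-prone analyses, masking is not workable, and those analyses should not be described as blinded. For the primary and ventilatory-assistance outcomes it is workable on two conditions that the plan does not secure: proning fields are withheld, and the set is all randomised patients by coded allocation.

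The size is one of procedure and reporting. No bias in the primary comparison has been demonstrated, and no power or sample-size figure depends on this. The probabilities above rest on assumed proning rates and independent binomial counts; they show only that rescue proning would not restore masking. The contradiction in 11b is the more serious defect nearby, and it must be settled first because it decides whether the primary analysis can be masked at all. The point merits a change to the plan but does not threaten the trial.

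**What to change.** Make the changes in this order.

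0. Reconcile section 11b so that the primary analysis includes all randomised patients, grouped by randomised allocation. Name the primary test in advance, which closes the chi-square or Fisher choice separately from masking.
1. Rewrite section 9e so that the primary and ventilatory-assistance outcomes are run and signed off on a locked file. The file holds a masked arm code, site, pre-randomisation variables and event dates (intubation, CPAP/BIPAP, death, last contact), and no proning fields. Someone other than the analyst should prepare it and hold the code.
2. Only after sign-off, merge the proning data for the tolerability, oxygenation, per-protocol and rescue-prone analyses, and report these as unblinded.

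Step 1 depends on step 0: if the any-proning set governed, a file without proning fields could not form the analysis set.

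The cost is revised wording in 9e and 11b and one additional data extract. The proning analyses must wait until the primary result is signed off.

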### ***10. Schedule of assessment***

#### ***a. Data collection and management***

Data will be collected using an electronic case report form hosted in UCD. Details of CRF attached in appendix B. No patient identifiers will leave hospital unit and all data sent to CRF at NUI Galway will be pseudoanonymised. A collaborative data sharing agreement with UCD and NUI Galway has been developed. Aggregated data will be shared with investigators of the Awake Prone Positioning in COVID Meta-Trial for interim analysis and Anonymised data without personal identifying features will be sent for final analysis and co-reporting of outcomes.

#### ***b. Data quality***

Data quality will be audited by the CRF at NUI Galway as responsibility of the study sponsor.

### ***11. Statistical Considerations***

#### ***a. Sample size***

From ICNARC data on patients admitted to ICU with COVID19, 60% required advanced respiratory support. From this, we propose a 60% intubation rate in this cohort as defined above and that proning will decrease it to 40%. From this, 97 patients per group for a beta of 0.2 and alpha 0.05, requiring the need to recruit 196 patients. Interim analysis of data will be conducted using aggregated data as part of the Awake Prone Positioning in COVID Meta-Trial.

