**c. *Experience with awake prone positioning in self-ventilating patients***

Prone position results in improved ventilation and blood flow ratios. In mechanically ventilated and often paralysed patients, proning requires a high nursing input and patients are at risk for pressure sores related to the position. These issues are less pertinent in patients who are self-ventilating. Proning self-ventilating patients is not commonly carried out as patients with reduced oxygenation generally require assisted ventilation. However, avoidance of mechanical ventilation by improving oxygenation may be importance in COVID19 as outcomes for patients who require mechanical ventilation are poor and resources become limited. We have noted improvement with proning in self ventilating patients at both ward level and in the ICU for patients with confirmed COVID19 and in a patient without COVID19 with ARDS.

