### **a. Withdrawal criteria**

- Patients cannot tolerate HFNC or prone position for 30 mins
- Patients experience any side effects during prone position, including vomit, dizzy, hypotension, etc.

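### The 80% power in section 11a is conditional: it assumes no crossover or loss beyond what the 60% and 40% rates already contain, and an uncorrected chi-square test, but the plan states neither condition

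*Combined protocol and SAP*

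**What the plan says.** Section 11a (Sample size) takes a 60% rate from ICU audit data and assumes an effect: "we propose a 60% intubation rate in this cohort as defined above and that proning will decrease it to 40" per cent. It then gives the size: "From this, 97 patients per group for a beta of 0.2 and alpha 0.05, requiring the need to recruit 196 patients". No allowance for crossover, non-adherence or loss is stated, and the test behind the calculation is not named.

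Three other places bear on this:

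- Section 11b (Analysis population) provides for crossover: "Patients who were rescue prone will be considered a protocol deviation and will be studied as a group". It also says that all analyses are by intention to treat.
- Section 9a (Withdrawal criteria) lists "Patients cannot tolerate HFNC or prone position for 30 mins", and also side effects during proning.
- Section 11b leaves the test open: "Qualitative or categorical variables are compared with the chi square test or the Fisher's exact test". No rule says which applies to the primary outcome.

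The trial is open label (sections 5a and 9e). In section 3c the investigators report their own favourable experience: "We have noted improvement with proning in self ventilating patients at both ward level and in the ICU".

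**The concern.** Under intention to treat, a control who is proned and a prone-arm patient who stops both count in the arm to which they were assigned. Each such patient pulls the two event rates together. A calculation with about two patients to spare cannot absorb much of this. If the rates in section 11a describe full separation of the arms, the planned analysis has less than the stated power, and a non-significant result could be reported as an 80%-powered negative when it was not.

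The open choice of test adds a smaller problem that needs no assumption about behaviour: one of the two permitted tests misses 80% at this sample size even if everyone adheres.

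**Working it through.** **Inputs from the documents.** Control rate 0.60, prone rate 0.40, alpha 0.05, power 0.80 (section 11a); allocation 1:1 (section 9d). The plan does not state sidedness. Two-sided is inferred, because a one-sided calculation gives 77 per group, or 86 with continuity correction.

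**Reproducing 97.** With p̄ = 0.50 and pooled variance under the null:

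n = [1.960·√(2·0.5·0.5) + 0.8416·√(0.24 + 0.24)]² / 0.20²
= (1.3859 + 0.5831)² / 0.04 = 96.9, so 97 per group.

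The arcsine method gives 96.8, also 97. The unpooled formula gives 94.2 and the continuity-corrected one 106.7. So 97 matches an uncorrected chi-square or its equivalent.

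**Slack.** 2 × 97 = 194. Recruiting 196 leaves 2 patients, or 2/196 = 1.0%.

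**Power as planned.** Power = Φ{[d√n − 1.960·√(2p̄(1−p̄))] / √(p₁(1−p₁) + p₂(1−p₂))}, with d = p₁ − p₂. At 98 per group this is Φ[(1.9799 − 1.3859)/0.6928] = Φ(0.857) = 80.4%. At 97 it is 80.0%.

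**Choice of test, full adherence, exact enumeration at 60% versus 40%:**

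| Per group | Uncorrected chi-square | Fisher's exact |
|---|---|---|
| 97 | 80.7% | 76.4% |
| 98 | 81.3% | 77.2% |

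**Dilution (rates assumed; the documents give none).** Let a fraction c of controls be rescue proned and take the prone risk, and a fraction s of the prone arm stop and take the control risk. Then p₁ = 0.60 − 0.20c, p₂ = 0.40 + 0.20s, and the difference is 0.20(1 − c − s). At 98 per group, by the formula above:

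| c (controls) | s (prone arm) | Rates | Power |
|---|---|---|---|
| 0 | 0 | 60% v 40% | 80.4% |
| 5% | 0 | 59% v 40% | 76.2% |
| 10% | 0 | 58% v 40% | 71.6% |
| 5% | 5% | 59% v 41% | 71.5% |
| 10% | 10% | 58% v 42% | 61.2% |

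If each crossover exchanges only half the effect, 5% in each arm gives 59.5% v 40.5% and 76.2% power, and 10% in each arm gives 59% v 41% and 71.5%.

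**Loss alone.** 5% loss leaves about 93 per group and 78.3% power.

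**The case against.** A reader might infer that the trial's intention-to-treat analysis does not have 80% power, or that its power is near 60%. The documents support neither statement.

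- **The 40% may already be net of stopping.** Section 9 has patients stay prone for as long as they can manage. Under such a regimen 40% can be read as the rate in everyone assigned to proning, with ordinary stopping included. Section 11a says that "proning will decrease it to 40" per cent is the result, which sounds like the effect of proning itself, but it does not settle the matter. This stands.
- **No crossover rate is given.** Classing rescue proning as a deviation provides for it without forecasting how often it happens. Section 3c is background experience, not a statement about controls. The exclusion of patients unlikely to manage 16 hours prone should limit early intolerance, and section 9d defines control as no proning. The figure near 60% needs 10% crossover in each arm with full exchange of effect. Full benefit from proning begun as rescue is a worst case. This stands.
- **Loss matters little.** 5% loss costs about two points, and the outcome is ventilation or death by day 28 in patients enrolled in hospital. This stands.
- **The gap between 194 and 196 may be innocent.** Blocks have length 4, and 196 is a multiple of 4 while 194 is not. That is plausible, though the plan does not say so.
- **Fisher's test is listed generically.** Section 11b does not select it for the primary outcome, and with about 40 to 60 patients expected in each cell there is no small-count reason to use it. That makes its use unlikely, but the plan does not rule it out.
- **The trial feeds a prospective meta-trial** (sections 5a and 10a), so a stand-alone reading of a negative result is less likely. This lessens the harm but does not correct the power statement.

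One part survives all of this. Even if 40% absorbs stopping in the prone arm, the 60% comes from ICU audit data and carries no stated allowance for rescue proning of trial controls.

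**Conclusion.** The concern holds in a limited form. The 80% is arithmetically right, but only for 60% versus 40% with no dilution beyond what those rates already contain, analysed by an uncorrected chi-square or its equivalent. The plan foresees rescue proning and intolerance, intends intention to treat, and states no allowance for either.

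The firm part is the choice of test: Fisher's exact test would put power at about 76% to 77% with perfect adherence. The conditional part is dilution. Rescue proning of controls alone at 5% or 10% would give about 76% or 72%, and crossover of 5% or 10% in each arm about 72% or 61%. These rates are assumptions, as is full exchange of effect; half exchange roughly halves the dilution. The rows with crossover in both arms apply to stopping only if 40% is a full-adherence rate.

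Two matters are taken as given here and are separate: that 60% is an intubation rate while the primary outcome also counts death, and that section 11b elsewhere describes groups by treatment received.

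**What to change.** The trial need not be enlarged. In section 11a:

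1. State that 80% power (98 per group, 196 in total) is for 60% versus 40% by two-sided uncorrected chi-square, with no crossover or loss.
2. Say whether 40% is the rate in everyone assigned to proning, net of non-adherence, or the rate under full adherence.
3. Add a short range, labelled as assumption with full exchange of effect: about 76% / 72% with 5% / 10% rescue proning among controls only, and about 72% / 61% with 5% / 10% in each arm. If 40% is already net of stopping, keep only the control-arm figures.
4. Make the per-group figure and the total agree (97 and 194, or 98 and 196), giving the reason if 196 is kept for blocking.

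In section 11b, name one test for the primary outcome: the uncorrected chi-square, preferably in a form stratified by site (Cochran-Mantel-Haenszel), because randomisation is stratified by site. State that Fisher's exact test will not be used for that outcome.

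The cost is protocol and SAP wording, and a stated power that looks less favourable. The sponsor should replace the illustrative rates with its own if it has any basis for them.

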#### ***b. Analysis population***

Data will be analysed on an intention to treat basis with all data for patients who consented to be involved included in baseline data analysis. Outcome data will be analysed for all patients who were positioned in the prone position for any length of time. A further per protocol analysis will be carried out on all patients who tolerated at least 1 hour of the daytime proning time and at least 2 hours of the night time proning period in any 24 hour period. Patients who were rescue prone will be considered a protocol deviation and will be studied as a group. Definition of the two groups: The

patients who receive the prone positioning are classified as prone positioning group. The patients who receive HFNC alone are classified as HFNC group. Comparisons between the two groups: Quantitative continuous variables are given as either means ( $\pm$ SDs) or medians (with inter-quartile ranges) are compared using the unpaired Student's t test or the Mann-Whitney test. Qualitative or categorical variables are compared with the chi square test or the Fisher's exact test. ANOVA for paired tests to compare the same variables collected at different time points are used. The cumulative probability of remaining on spontaneous breathing are compared with the Kaplan-Meier estimate of survival and the log-rank test to compare the two groups. Univariate and multivariate analyses of risk factors for PP failure are performed with logistic regression. All analyses are in intention to treat, and the level of significance is set at 0.05.

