#### ***d. Allocation and Randomisation***

Within 6 hr of fulfilling inclusion criteria, a patient will be randomly allocated either to the prone positioning group or the control group (HFNC alone with no prone positioning therapy). Patients will be randomly allocated to either arm of the study at a ratio based on a 1:1 basis using a REDCAP randomisation process. Randomization will be stratified by site using tables of random permutations using the RECAP database for randomization. The random block length is 4, and random numbers are generated by computer.

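### Section 11b promises intention to treat but limits outcome analysis to proned patients and defines the groups by treatment received

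*Combined protocol and SAP*

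**What the plan says.** Section 9d sets up the comparison by allocation: "a patient will be randomly allocated either to the prone positioning group or the control group". The primary outcome (section 6a) is invasive ventilation or death by 28 days.

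Section 11b then makes these statements:

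- It opens with "Data will be analysed on an intention to treat basis", but attaches the full consented population only to the baseline data.
- The next sentence reads "Outcome data will be analysed for all patients who were positioned in the prone position for any length of time". No other sentence names an outcome population.
- A further, separate per-protocol set takes patients who "tolerated at least 1 hour of the daytime proning time and at least 2 hours of the night time proning period" in any 24-hour period.
- On rescue proning: "Patients who were rescue prone will be considered a protocol deviation and will be studied as a group".
- The groups are defined by treatment received: "patients who receive the prone positioning are classified as prone positioning group" and "The patients who receive HFNC alone are classified as HFNC group".
- It closes with "All analyses are in intention to treat".

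Section 9a lists inability to tolerate HFNC or the prone position for 30 minutes as a withdrawal criterion. It does not say whether withdrawn patients remain in the outcome analysis.

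**The concern.** An analyst cannot follow every sentence of section 11b at once, and the choice between them changes who is counted in the primary comparison. At least three readings can be defended from the text:

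- **A, literal.** Outcomes are analysed only in proned patients. No un-proned control is left, so there is no randomised comparison.
- **B, as treated.** Never-proned patients in the prone arm count as HFNC. Rescue-proned controls no longer fit the HFNC definition, and the text does not say whether they move, drop out or stay.
- **C, modified intention to treat.** Never-proned patients are removed from the prone arm only.

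Patients too ill or distressed to be proned, and controls ill enough to be rescue-proned, may well have a different prognosis from the rest. Removing or regrouping them after randomisation can bias the result in either direction. Because the trial is open label, who gets proned can itself depend on clinical course. If the rule is left unsettled, it could also be chosen after the data are seen.

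**Working it through.** **The text.** The any-length-of-time sentence cannot be the per-protocol set, because that set is introduced separately as a further analysis. The group definitions speak of receipt, while section 9d speaks of allocation. No section says that receipt means allocation, or which sentence of 11b prevails. The contradiction therefore stands without any arithmetic; the figures below only show what it could do.

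**The plan's own figure.** Section 11a uses 60% vs 40%, alpha 0.05 and beta 0.2. With a two-sided test and pooled variance under the null:

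n = [1.960·√(2·0.5·0.5) + 0.842·√(0.24 + 0.24)]² / 0.20² = 96.9, so 97 per group, as stated.

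The plan recruits 196, or 98 per arm. The null SE is √(0.25·2/98) = 0.0714 and the alternative SE is √(0.24·2/98) = 0.0700. Power is Φ[(0.20 − 1.960·0.0714)/0.0700] = 80.4%.

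**Assumptions (not in the document).** A share f of an arm is affected and has risk r. The main range is f = 10–20% and r = 60–90%; one milder row at 5% is added. The same normal approximation is used throughout, with pooled SE for the critical value and unpooled SE for the spread.

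**Never-proned patients, no true effect (60% in both arms).**

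- Remaining prone group: (0.60 − f·r)/(1 − f), n = 98(1 − f).
- Dropped (reading C): control stays at 0.60, n = 98.
- Regrouped (reading B): HFNC = (0.60 + f·r)/(1 + f), n = 98(1 + f).

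| f | r | Dropped: prone vs control | Two-sided rejection | Regrouped: prone vs HFNC | Two-sided rejection |
|---|---|---|---|---|---|
| any | 60% | 60.0% vs 60.0% | 5.0% | 60.0% vs 60.0% | 5.0% |
| 5% | 80% | 58.9% vs 60.0% | 5.3% | 58.9% vs 61.0% | 5.9% |
| 10% | 80% | 57.8% vs 60.0% | 6.1% | 57.8% vs 61.8% | 8.9% |
| 20% | 80% | 55.0% vs 60.0% | 10.3% | 55.0% vs 63.3% | 21.5% |
| 20% | 90% | 52.5% vs 60.0% | 17.0% | 52.5% vs 65.0% | 41.7% |

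Last row: (0.60 − 0.18)/0.80 = 0.525 and (0.60 + 0.18)/1.20 = 0.650.

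**Rescue-proned controls, true effect 60% vs 40%.** These patients are part of the control arm's 60%.

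- Remaining control: (0.60 − f·r)/(1 − f), n = 98(1 − f).
- Dropped: prone stays at 0.40, n = 98.
- Reclassified: prone = (0.40 + f·r)/(1 + f), n = 98(1 + f).

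| f | r | Dropped: difference | Power | Reclassified: difference | Power |
|---|---|---|---|---|---|
| 10% | 60% | 20.0 points | 78% | 18.2 points | 72% |
| 10% | 80% | 17.8 points | 68% | 14.1 points | 50% |
| 20% | 80% | 15.0 points | 51% | 8.3 points | 21% |
| 20% | 90% | 12.5 points | 38% | 4.2 points | 8% |

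Power here is rejection in favour of prone; counting both tails, the last figure is 8.8%.

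**Both together.** The two biases can partly cancel. With no true effect, 10% never-proned at 90% risk and 10% rescue-proned at 80% risk, all regrouped, the prone group becomes 0.60 − 0.09 + 0.08 = 59.0% and HFNC becomes 0.60 + 0.09 − 0.08 = 61.0%.

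**Per-protocol set.** Only a direction can be given. Qualifying in any 24-hour period gives patients who stay event-free longer more chances to qualify, and the rule cannot be applied to controls.

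**The case against.** The best defence is that intention to treat is stated twice, the second time as a closing sentence covering all analyses, and that section 9d defines the same groups by allocation. Receipt may then be loose wording for allocation. The any-length-of-time sentence may have been meant for secondary outcomes that exist wholly or mainly in proned patients, such as tolerance time and oxygenation before and after proning. This is plausible, and the closing sentence carries as much force as the others. But none of it is written down. If the sentence is taken to describe only the prone arm, it still removes never-proned patients from that arm, which is not intention to treat.

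Four further points have some force:

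- **Masked analysis.** Section 9e has the analysis data labelled group 1 and group 2. That is a partial safeguard against choosing a rule by its result. It does not settle who belongs in each group, and proning data could reveal the arm.
- **Brief proning.** Someone proned for less than 30 minutes was still proned for some length of time, so the outcome sentence keeps them. The gap left by section 9a concerns never-proned and HFNC-intolerant patients, and whether withdrawal ends follow-up.
- **Scale.** Any proning at all is a low bar, and section 7c excludes patients unlikely to tolerate the position, so 20% never-proned may be high. The milder rows deserve more weight than the corners.
- **Rescue proning.** Section 11b does not state the arm or timing of rescue-proned patients. Studying them as a group may mean no more than a supplementary description, so moving them into the prone group is one possible handling and not a clear instruction.

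These points limit the likely size of the problem. They do not remove the contradiction.

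**Conclusion.** The concern holds and must be fixed. Section 11b contradicts itself on the population and grouping for the primary outcome, and only its intention-to-treat sentences preserve the randomised comparison. Reading A leaves no control comparison.

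For the other readings, over the assumed 10–20% affected and 60–90% risk, mishandling never-proned patients gives a spurious benefit of 0 to 7.5 points (rejection 5.0% to 17.0%) if they are dropped. If they are regrouped, it is 0 to 12.5 points (5.0% to 41.7%). Mishandling rescue-proned controls cuts power from 80.4% to between 78% and 38% if they are dropped, or between 72% and 8% if they are reclassified.

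The upper ends need 20% affected at 90% risk, and the bias under no true effect vanishes if affected patients have average risk. The textual contradiction depends on none of these assumptions.

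**What to change.** Replace the outcome-population sentence in section 11b with wording such as: *All outcomes are analysed in all randomised patients, in the arm to which they were randomised, whatever positioning was received; rescue-proned controls remain in the control arm.* Then:

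- State that patients meeting the section 9a withdrawal criteria stay in this analysis.
- Delete the definition of groups by treatment received.
- Report rescue proning descriptively as a protocol deviation.
- Label the any-proning and per-protocol analyses supportive and non-randomised. A complier-average estimate is optional, with its assumptions stated.
- Define the day and night proning periods used in the per-protocol rule, which appear nowhere else in the document. Reconcile them with the durations in section 7c (16 hours, as an eligibility screen) and section 9 (at least 30 minutes, per session).

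The change should be made before outcome data are examined by arm. It is wording only, with no new patients or data, and the planned size is unchanged under the plan's own inputs.

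The cost is the usual dilution. If non-adherent prone-arm patients keep a 60% risk, the prone risk is 0.40(1 − f) + 0.60f, and power falls from 80.4% to 71.6% at f = 10% and 61.2% at f = 20%. If the same share of controls also crosses over with full benefit, the control risk is 0.60(1 − f) + 0.40f, and power is 61.2% and 38.9%.
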